8.2.2.6 Peak pain relief

The peak pain relief score for each subject will be identified using the description in [Section 7.9.12](#). The data for this endpoint will be analyzed using a proportional odds model (an extension of logistic regression model) which allows for an ordinal response variable with more than two categories. This model will include factors site, treatment and baseline pain intensity.

8.2.2.7 Time to peak pain relief

Time to peak pain relief will be summarized using Kaplan-Meier methods. The definition and censoring rules are described in [Section 7.9.13](#). Treatments will be compared to placebo using a log-rank test which will compare the survival distributions of the treatments.

8.2.2.8 Time to first perceptible pain relief

Time to first perceptible pain relief will be summarized using Kaplan-Meier methods. The definition and censoring rules are described in [Section 7.9.14](#). Treatments will be compared to placebo using a log-rank test which will compare the survival distributions of the treatments.

8.2.2.9 Time to meaningful pain relief

Time to meaningful pain relief will be summarized using Kaplan-Meier methods. The definition and censoring rules are described in [Section 7.9.15](#). Treatments will be compared to placebo using a

log-rank test which will compare the survival distributions of the treatments.

8.2.2.10 Proportion of subjects using rescue medication

The definition of rescue medication use is presented in [Section 7.9.16](#). The proportion of subjects using rescue medication for pain will be analyzed using logistic regression. The logistic regression model will include factors site, treatment and baseline pain intensity.

8.2.2.11 Time to first use of rescue medication (duration of analgesia) following each dose of IP

Time to time to first use of rescue medication will be summarized using Kaplan-Meier methods. Censoring will be applied as described in [Section 7.9.17](#). Treatments will be compared to placebo using a log-rank test which will compare the survival distributions of the treatments.

8.2.2.12 Total use of rescue analgesia over 0 to 24 hours and over 0 to 48 hours

The frequency of use of rescue analgesia will be calculated for each subject over 0 to 24 and 0-48 hours. The differences in total use of rescue analgesia between the treatment groups and placebo will be compared using an analysis of covariance (ANCOVA) model, which will include treatment and site as main effects and baseline pain intensity as the covariate. The last square (LS) mean, standard error (SE) and 95% confidence interval (CI) for each treatment group will be estimated for each time interval 0-24 hours and 0-48 hours. In addition, the mean (LS mean) difference between each treatment and placebo, SE, p-value and the associated 95% CI will also be computed. Descriptive summaries (including mean, SD, median, minimum and maximum) will also be presented by treatment group.

8.2.2.13 NRS pain intensity difference (NRS PID) at each scheduled time point after Time 0

The PID at each scheduled time point will be calculated using the formula specified in [Section 7.9.6](#). The differences in NRS PID between the treatment groups and placebo will be compared using an analysis of covariance (ANCOVA) model, which will include treatment and site as main effects and baseline pain intensity as the covariate. The last square (LS) mean, standard error (SE) and 95%

confidence interval (CI) for each treatment group will be estimated. In addition, the mean (LS mean) difference between each treatment and placebo, SE, p-value and the associated 95% CI will also be computed. Descriptive summaries (including mean, SD, median, minimum and maximum) will also be presented by treatment group.

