4.3. Method of Assigning Subjects to Treatment Groups

Eligible subjects meeting all study entry criteria will be randomly allocated in a 1:1:1 ratio to 1 of the 3 treatment groups.

The randomization schedule will be computer generated by using a permuted block algorithm and will randomly allocate the investigational produce (IP) to randomization numbers. The randomization numbers will be provided to the drug packager who will prepare blinded drug kits with all twelve (12) doses identified to maintain the drug blinding. The randomization schedule will be prepared by the sponsor or sponsor's representative before the start of the study. No one involved in the study performance will have access to the randomization schedule before official unblinding of treatment assignment. No subject will be randomized into this study more than once.

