8.5.3.2. Secondary Efficacy Analysis

The secondary endpoints NRS SPID-4, NRS SPID-8, NRS SPID-24, TOTPAR-4, TOTPAR-8, TOTPAR-24, TOTPAR-48, time to use of rescue analgesia, and total use of rescue analgesia will be analyzed similarly to the primary endpoint. The NRS pain intensity and the pain relief scores at each time point will also be summarized descriptively. Time to event endpoints (time to onset of analgesia, time to peak pain relief, time to perceptible relief, time to meaningful relief, and time to first rescue medication) will be analyzed using Kaplan-Meier methods. Peak pain relief score, average time to use of rescue of analgesia following a dose of IP, proportion of subjects using rescue medication, and the subject's global evaluation will be analyzed using chi-square, Fishers exact, or logistic regression techniques as appropriate. No formal statistical inferences will be made on any secondary endpoints. Details of statistical analyses will be described in the SAP that will be finalized before database lock and unblinding.

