4. SAMPLE SIZE DETERMINATION AND RATIONALE, STATISTICAL POWER, AND SIGNIFICANCE LEVEL

A total of 45 subjects are planned to be enrolled for the study. A sample size of 15 subjects per treatment group will provide $\geq 80\%$ power to detect a minimal standardized effect size of 0.5 between the 100 μg q4h, 200 μg q4h active treatment arms, and placebo in NRS SPID-48 using a 3-group analysis of covariance (ANCOVA) with baseline NRS score as the covariate with a 0.05 two-sided significance level (EAST v6).

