7.9.16 Rescue Medication Use

Total use of rescue medication is the number of times that a subject used rescue medication for pain during the specified time periods (0-24h and 0-48h). The proportion of subjects taking rescue medication for pain during each period will also be presented. A subject taking any amount of rescue medication during the specified period will be counted in this proportion.

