8.2.2.3 Subject's global evaluation of study drug

Subject's global evaluation of study drug will be analyzed using a proportional odds model (an extension of the logistic regression). This method allows for an ordinal response variable with more than two categories. This model will include factors site, treatment and baseline pain intensity.

8.2.2.4 Time to onset of analgesia (measured as time to perceptible pain relief confirmed by meaningful pain relief using the 2-stopwatch method)

Time to onset of analgesia will be summarized using Kaplan-Meier methods. The definition and censoring rules are described in [Section 7.9.11](#). Treatments will be compared to placebo using a log-rank test which will compare the survival distributions of the treatments.

8.2.2.5 Pain relief score on a 5-point categorical scale at each scheduled time point after Time 0

The differences in pain relief between the treatment groups and placebo will be compared using a proportional odds model (an extension of logistic regression model) which allows for an ordinal response variable with more than two categories. This model will include factors site, treatment and baseline pain intensity.

In addition, the pain relief scores at each time point will also be summarized descriptive in tables and also presented as by-subject listings.

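### SAP 8.2.2.10 names logistic regression for the proportion using rescue, at 15 subjects per arm, with no estimator, test or fallback if every placebo subject uses rescue

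*SAP*

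**What the plan says.** SAP 8.2.2.10 gives one method for this endpoint: "The proportion of subjects using rescue medication for pain will be analyzed using logistic regression". It adds only the terms: "The logistic regression model will include factors site, treatment and baseline pain intensity". It does not say how the model is estimated, which test of treatment is reported, or what happens if an arm has 0% or 100% users.

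Protocol 8.5.3.2 was wider. For a group of endpoints that includes this one, it says that they "will be analyzed using chi-square, Fishers exact, or logistic regression techniques as appropriate". It leaves details to the SAP and states that secondary endpoints carry no formal inference.

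The endpoint is defined in SAP 7.9.16 for 0-24 h and 0-48 h: "A subject taking any amount of rescue medication during the specified period will be counted in this proportion". On size, SAP section 4 says "A sample size of 15 subjects per treatment group will provide" the stated power, and protocol 4.3 has subjects "randomly allocated in a 1:1:1 ratio to 1 of the 3 treatment groups". Neither document states an expected rescue rate.

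**The concern.** The endpoint is generous: one dose of rescue in 24 or 48 hours makes a subject a user. Entry requires a pain score of at least 4, and protocol 1.1 describes pain after this operation as lasting several days at moderate to severe intensity. A placebo arm in which everyone takes rescue is therefore a realistic outcome at 15 subjects.

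If that happens, ordinary maximum likelihood has no finite estimate for either active-placebo contrast (quasi-complete separation). The usual software output is then a huge coefficient, a far larger standard error and a Wald p-value near 1, even when many fewer fentanyl subjects needed rescue. This is among the outcomes most favourable to the drug.

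Because the SAP names no test, the choice among Wald, likelihood-ratio, Firth and Fisher could also be made after the data are seen, and those methods can give very different answers on the same counts.

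**Working it through.** **Inputs.** From the documents: 15 per arm, three arms, 1:1:1 (SAP 4; protocol 4.3); terms site, treatment and baseline pain (SAP 8.2.2.10); any use counts (SAP 7.9.16). Assumed, because the documents give no figure: true rescue rates and, for simulation, a 10:5 site split per arm and baseline scores of 4 to 9.

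**Figure to reproduce.** None. The plan states no rate, power or p-value for this endpoint; its 80% power figure concerns SPID-48.

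**Step 1: chance that all 15 placebo subjects are users.** P = p^15.

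| Assumed true rate | P(15/15) |
|---|---|
| 80% | 0.035 |
| 90% | 0.206 |
| 95% | 0.463 |
| 98% | 0.739 |

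**Step 2: why the estimate fails.** With placebo at 15/15 and no covariates, the placebo part of the log-likelihood is 15·log(π). It keeps rising as π approaches 1, so the placebo log-odds runs to +∞ and each active-placebo log odds ratio to −∞. With both active arms at 9/15, the converged fit gave a coefficient of −19.8 with standard error 6294. Then z = −19.8/6294 = −0.003 and p = 0.997.

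**Step 3: the Wald p-value depends on the stopping point.** Site and baseline were in the model, placebo was fixed at 15/15, and 400 data sets were simulated for each of three pairs of true active rates (80%/70%, 60%/40%, 30%/20%). Median Wald p was 0.85 to 0.88 after 10 iterations, 0.94 to 0.95 after 12, and 0.996 at convergence. It barely moved with the true active rate.

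**Step 4: Fisher on the same counts.** With placebo at 15/15 and k non-users in the active arm, the two-sided p is 2·C(15,k)/C(30,k).
- 10/15 (k = 5): 2 × 3003/142506 = 0.042
- 9/15 (k = 6): 2 × 5005/593775 = 0.017
- 8/15 (k = 7): 2 × 6435/2035800 = 0.006

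**Step 5: likelihood-ratio test from the same model (no covariates), active 10/15.**
- Separate arms: 10·ln(10/15) + 5·ln(5/15) = −9.548 (placebo contributes 0).
- Pooled 25/30: 25·ln(25/30) + 5·ln(5/30) = −13.517.
- Statistic: 2 × (13.517 − 9.548) = 7.94 on 1 df, p = 0.005.

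**Step 6: the four methods side by side** (placebo 15/15, no covariates, both active arms in the model):

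| Active arm | Wald, converged | Likelihood ratio | Firth | Fisher |
|---|---|---|---|---|
| 10/15 | 0.998 | 0.005 | 0.016 | 0.042 |
| 9/15 | 0.997 | 0.002 | 0.006 | 0.017 |
| 8/15 | 0.997 | 0.0006 | 0.002 | 0.006 |
| 5/15 | 0.997 | 0.00001 | 0.0001 | 0.0002 |

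**Step 7: behaviour over repeated trials** (simulation, 15 per arm; the model-based tests are adjusted for site and baseline; the placebo count varies at random):

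| Placebo v active rate | Wald | Firth | Fisher |
|---|---|---|---|
| 95% v 70% | 10% | 39% | 28% |
| 95% v 60% | 16% | 65% | 50% |

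Entries are the share of trials with p < 0.05. The likelihood-ratio test rejects more often (57% and 76% in these two cases). However, with no true difference it rejected in roughly 5% to 11% of trials, depending on the assumed rate, while Firth stayed below the nominal 5%.

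**The case against.** Several stronger readings are tempting, and the documents do not support them.

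- **That the SAP fixes maximum likelihood with a Wald test.** It says only logistic regression. Ordinary maximum likelihood with Wald output is the usual software default, but that is an inference from silence.
- **That the treatment test fails whatever the true difference.** This is true of the Wald test alone. Likelihood-ratio, Firth and exact methods all remain informative with placebo at 15/15. The likelihood-ratio test does not supply a finite odds ratio, however, and its error rate can exceed 5% at this size.
- **That a real difference would be lost.** Protocol 8.5.3.2 makes no formal inference on secondary endpoints. SAP 7.9.16 also presents the raw proportions, so 15/15 against 9/15 would be seen. Time to first rescue (Kaplan-Meier, log-rank) and total use (ANCOVA) are reported too, and neither breaks down when all placebo subjects use rescue.
- **That the SAP contradicts the protocol by dropping Fisher's test.** The protocol gives a menu for several endpoints and leaves the details to the SAP. Choosing one listed method is allowed; what is missing is the fallback.
- **That the proportional odds model in SAP 8.2.2.5 has the same weakness.** There, "The differences in pain relief between the treatment groups and placebo will be compared using a proportional odds model". An empty category in one arm does not cause separation: relief counts of 8/4/3/0/0 against 3/3/4/3/2 gave a finite estimate of 1.85 (SE 0.73, p = 0.011). Failure would need something like a whole arm in one extreme category.

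It is also fair to say that the trigger is conditional and its probability rests on an assumed rate. These points limit the consequence. They do not remove the gap, because a non-estimable odds ratio is a poor description as well as a poor test.

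**Conclusion.** The point holds as a gap in specification with a cheap and better alternative. If all 15 placebo subjects use rescue, the unqualified model yields no finite odds ratio, and its default p-value reflects the stopping rule of the software rather than the data. The chance of that runs from 3.5% to 74% over assumed true placebo rates of 80% to 98%; the documents do not narrow this range. On identical counts (15/15 v 10/15) the reported p could be 0.998, 0.042, 0.016 or 0.005 according to a choice that the SAP leaves open.

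The consequence is confined to one descriptive secondary endpoint. The primary analysis of SPID-48 is untouched. The power and error figures rest on the assumed rates, site split and baseline distribution. The Fisher values and the p^15 formula need no such assumptions, although p itself is assumed.

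**What to change.** In SAP 8.2.2.10, before unblinding, specify:

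- Firth-penalised logistic regression with the terms already planned (site, treatment, baseline pain intensity), for both 0-24 h and 0-48 h;
- penalised likelihood-ratio p-values and profile-likelihood 95% confidence intervals for each dose against placebo;
- Fisher's exact test for each dose against placebo as a supporting analysis, which brings back an option that the protocol lists.

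Use this method whatever the data show, so that no switch depends on the observed counts. Leave SAP 8.2.2.5 as it is.

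The cost is a few lines of SAP text and standard SAS options; no new data are needed. The downsides are small: Firth shrinks the odds ratio slightly, and the supporting Fisher test is somewhat conservative and does not adjust for site or baseline pain.

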8.2.2.14 NRS pain intensity score at each scheduled time point

The differences in NRS pain intensity between the treatment groups and placebo will be compared using an analysis of covariance (ANCOVA) model, which will include treatment and site as main effects and baseline pain intensity as the covariate. The last square (LS) mean, standard error (SE) and 95% confidence interval (CI) for each treatment group will be estimated. In addition, the mean (LS mean) difference between each treatment and placebo, SE, p-value and the associated 95% CI will also be computed. Descriptive summaries (including mean, SD, median, minimum and maximum) will also be presented by treatment group.

In addition, the pain intensity scores at each time point will also be summarized descriptively in tables and figures.

8.2.3 Analysis of Safety Data

The safety population is the population for all safety assessments. No imputation will be used in the safety assessments. No inferential statistics are planned. No formal inferential analyses will be conducted for safety variables.

For continuous variables data will be summarized by treatment using n, mean, SD, minimum and maximum values. For categorical variables data will be summarized by treatment using frequency and percentage.

8.2.4 Adverse Events

Adverse events will be classified by system organ class (SOC) and preferred term (PT) according to the most recent MedDRA dictionary (Version 19.1 or higher).

All adverse events that occur on or after the date of first administration of clinical trial treatment until the end of study procedures are completed will be listed and summarized, using frequency

counts and percentages, by treatment group.

- Overall (*i.e.*, regardless of severity or relationship to treatment)
- By severity grade (mild, moderate, severe,)
- By relationship to clinical trial treatment (definitely related, probably related, possibly related, unlikely related, not related)

Unless otherwise specified, at each level of subject summarization, a subject will be counted only once. If there is more than one occurrence of an event, the event of the worst severity or the worst-case relationship category will be summarized.

AEs leading to premature discontinuation of clinical trial treatment, AEs of special interest, AEs that lead to study discontinuation, AEs that lead to death and Serious Adverse Events (SAEs) will also be summarized by treatment group and relationship. Adverse Events leading to premature discontinuation of clinical trial treatment will be defined as any adverse event with an Action Taken equal to “study drug discontinued” or “drug withdrawn”.

8.2.5 Clinical Laboratory Evaluations

Laboratory data is only collected for the screening visit. All available results of the clinical laboratory evaluations (e.g., Hematology, Chemistry, and Urinalysis) will be listed and descriptive summaries (mean, SD, median, minimum and maximum) of actual (absolute) values will be presented for clinical laboratory values for each treatment group.

8.2.6 Serum Pregnancy Test

All the results for serum pregnancy test will be presented as a by-subject listing.

8.2.7 Physical Examination / Oral Examination

The number and percentage of subjects with normal and abnormal findings in the physical and oral examinations at the Follow-up or Early Termination Visit will be displayed for each treatment group. All physical/oral examination findings will also be presented as a by-subject listing.

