4. TREATMENTS

4.1. Treatments Administered

Eligible subjects meeting all study entry criteria will be randomly allocated in a 1:1:1 ratio to one of the following treatments containing active or placebo administered up to 6 doses per day as shown in the table below:

Table 1: Study Treatment Regimens

Treatment group	Day 1						Day 2					
	Dose 1	Dose 2	Dose 3	Dose 4	Dose 5	Dose 6	Dose 1	Dose 2	Dose 3	Dose 4	Dose 5	Dose 6
100 µg	100 µg	100 µg	100 µg	100 µg	100 µg	100 µg	100 µg	100 µg	100 µg	100 µg	100 µg	100 µg
200 µg	200 µg	200 µg	200 µg	200 µg	200 µg	200 µg	200 µg	200 µg	200 µg	200 µg	200 µg	200 µg
Matching Placebo	P	P	P	P	P	P	P	P	P	P	P	P

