6.2.2. Physical and Oral Examinations

A complete physical examination (excluding the genitourinary examination) will be performed at Screening. An abbreviated physical examination will be performed at the Follow up Visit.

An oral cavity examination will be performed at Screening, on Day 1 prior to and one hour after first dose, and at the Follow up Visit. The oral examination at Screening and prior to first dose will exclude subjects with any active infection, mucositis, cold sores, viral lesions, local irritation, or periodontal disease of the oral cavity. In addition, subjects with recent (within 1 year) piercing of the tongue or anywhere in the oral cavity will be excluded. If there is a recent history of significant dental disease, the investigator may decide to exclude the subject. The oral examinations on Day 1 one hour after first dose and at the Follow up Visit will check for mucositis and local irritation.

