7.5. Interim Visits

Subjects should contact the study site if they experience any problems prior to the Follow-up Visit, and an interim visit will be arranged promptly as needed.

Table 2: Schedule of Assessments

	Screening (Days -28 to -1 before surgery)	Surgery Day 0	Treatment Period			Follow-up Day 7 ± 2 days (5 to 9 days after surgery) or Early Withdrawal
			Day 1 (Baseline; before dosing)	Day 1 First dose (Time 0)	Days 2 and 3 Subsequent doses	
Written informed consent	X					
Inclusion/exclusion criteria	X	X				
Demographics	X					
Medical history	X	X ^a				
Physical examination ^b	X					X
Oral examination ^c	X			X		X
Vital signs ^d	X	X	X	X	X	X
Height, weight, and body mass index	X					
Pulse oximetry ^e	X		X	X	X	
12-lead electrocardiogram ^f	X		X	X	X	
Clinical laboratory tests (hematology, chemistry, urinalysis)	X					
Pregnancy test for female subjects ^g	X	X				
Urine drug screen ^h	X	X				
Alcohol breathalyzer test		X				
X-ray and podiatric examination ⁱ	X					
First metatarsal bunionectomy procedure		X				
Discontinue anesthetic block at approximately 3:00 AM ^j			X			
Assign randomization number			X			
Pain assessments ^k			X	X	X	X
Administer study drug ^l				X	X	X

	Screening (Days -28 to -1 before surgery)	Surgery Day 0	Treatment Period			Follow-up Day 7 ± 2 days (5 to 9 days after surgery) or Early Withdrawal
			Day 1 (Baseline; before dosing)	Day 1 First dose (Time 0)	Days 2 and 3 Subsequent doses	
Start stopwatches for perceptible and meaningful pain relief ^m			X			
Subject's global evaluation of study drug ⁿ					X	
Concomitant medications	X	X	X	X	X	X
Adverse events		X	X	X	X	X
Dispense outpatient pain medication and outpatient subject diary ^o					X	
Discharge subject from the study site ^p					X	
Collect and review diary for completion						X

Abbreviations: ET=early termination; NRS=numeric rating scale

a Medical history should be reviewed for any changes since Screening.

b A complete physical examination (excluding the genitourinary examination) will be performed at Screening. An abbreviated physical examination, including an examination of the subject's surgical site, will be performed at the Follow-up Visit.

c The postdose oral examination should be conducted 1 hour (±10 minutes) after dosing.

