8.2. Safety Endpoints

The safety endpoints are the incidence of treatment-emergent adverse events (TEAEs), physical and oral examination findings, and changes in vital signs, pulse oximetry, and ECG measurements.

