8.5.4.5. Physical and Oral Examination Findings

The number and percentage of subjects with normal and abnormal findings in the physical and oral examinations at the Follow-up or Early -Withdrawal Visit will be displayed for each treatment group. New and worsening abnormal physical and oral examination findings during the study will be entered as AEs and analyzed within the AE tables.

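### The dedicated oral examination table leaves out the one-hour post-dose exam, pools Early Termination with Follow-up, and makes no use of the pre-dose exam

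*SAP*

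**What the plan says.** Protocol 8.2 names as safety endpoints the incidence of treatment-emergent adverse events together with "physical and oral examination findings, and changes in vital signs, pulse oximetry, and ECG measurements".

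Protocol 6.2.2 schedules the oral exam at Screening, "on Day 1 prior to and one hour after first dose, and at the Follow up Visit". It gives the last two a purpose: they "will check for mucositis and local irritation". Footnote c of protocol Table 2 fixes the timing: "The postdose oral examination should be conducted 1 hour (±10 minutes) after dosing". The Follow-up or Early Withdrawal column of that table also carries an oral exam.

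For the analysis, protocol 8.5.4.5 plans this: "The number and percentage of subjects with normal and abnormal findings in the physical and oral examinations at the Follow-up" or early withdrawal visit, by treatment group. It adds that a new or worse finding is recorded as an adverse event and counted in those tables. SAP 8.2.7 repeats the first part, with normal and abnormal "findings in the physical and oral examinations at the Follow-up or Early Termination Visit will be displayed for each treatment group", and promises a by-subject listing of all exams. It does not repeat the adverse event rule.

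**The concern.** The product is sprayed repeatedly under the tongue, so local irritation is a risk specific to its route. The one scheduled exam that looks for it during dosing has no row in the table that reports the endpoint. The pre-dose exam, which is the natural comparator, has none either, so a plain normal/abnormal count cannot separate an old finding from a new one.

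The row that does exist joins two visits at very different distances from exposure. If one arm has more withdrawals, its row contains more exams made near a spray. A difference between arms, or the lack of one, could then reflect when the mouths were examined.

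The SAP treats its other scheduled safety measures differently. ECG abnormalities (8.2.8) are summarised by time point, and vital signs with pulse oximetry (8.2.9) by time point with change from baseline.

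**Working it through.** **1. Exams scheduled against exams tabulated.**
- Screening: listing only.
- Day 1 before the first dose: listing only.
- Day 1, one hour after the first dose: listing only.
- Early withdrawal: tabulated, pooled with Follow-up.
- Follow-up, Day 5 to 9: tabulated, pooled with early withdrawal.

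Of the two exams that protocol 6.2.2 assigns to mucositis and irritation, one reaches the table, and it is mixed with another visit.

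**2. Dose count.** Protocol 4.1 has study drug "administered up to 6 doses per day" over two days: 6 × 2 = 12. Every 4 hours from 0 to 44 h gives 44/4 + 1 = 12. Both agree with protocol 4.3, "blinded drug kits with all twelve (12) doses identified". A scheduled post-dose exam follows the first dose only: 1/12 = 8.3% for a subject who takes all twelve, and a larger share for one who takes fewer.

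**3. Time from last spray to Follow-up, for a completer taking twelve doses.** Inputs: block stopped at about 03:00 on Day 1 and first dose within 9 hours (protocol 7.3.1 and 7.3.2); Follow-up on Day 5 to 9. Assumption: clinic visits between 08:00 and 18:00. The 10-minute windows are ignored.
- Time 0 lies between 03:00 and 12:00 on Day 1. Adding 44 h puts the twelfth dose between 23:00 on Day 2 and 08:00 on Day 3.
- Shortest gap: 08:00 Day 3 to 08:00 Day 5 = 48 h = 2.0 days.
- Longest gap: 23:00 Day 2 to 18:00 Day 9 = 163 h = 6.8 days.
- Midday visit on Day 7: 100 h to 109 h = 4.2 to 4.5 days.

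A subject who stops taking doses sooner has a longer gap. Protocol 7.3.2 has dosing run through 48 hours. A dose at 48 h would be the thirteenth, which does not fit a twelve-dose kit, so those passages need reconciling. It does not change the argument here.

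**4. What pooling does.** Protocol 3.3 asks for the end-of-study evaluations at discontinuation where possible, so a withdrawal exam can fall inside the 48-hour dosing period. Suppose two arms of n = 15 have k1 and k2 withdrawals and the same true finding rates, pE at withdrawal and pF at Follow-up. The expected count in the pooled row is k·pE + (15 − k)·pF. The difference between arms is then (k1 − k2)(pE − pF), although the arms do not differ.

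The documents give none of these four quantities. What follows without them is a bound: because pE − pF cannot exceed 1 in size, each extra withdrawal moves the expected count by at most one subject, or 1/15 = 6.7 percentage points. The difference vanishes if withdrawals are equal or the two rates are equal.

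**5. Why the number examined matters.** With 0 findings in 15 exams, the one-sided 95% upper limit is 1 − 0.05^(1/15) = 18%. With 0 in 10 it is 1 − 0.05^(1/10) = 26%. A row that does not say how many were examined at that time hides this difference.

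**The case against.** A reader might infer that the trial cannot show local irritation by arm at all. The documents do not support that. Protocol 8.5.4.5 turns any new or worse oral finding into an adverse event. Protocol 8.5.4.1 and SAP 8.2.4 tabulate adverse events by arm, and the SAP counts every event from the date of first dose, so a one-hour finding is included. Nothing in the SAP withdraws that rule. All exams are listed, and with 45 subjects a count by arm can be made by hand after unblinding.

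For irritation and mucositis specifically, protocol 6.2.2 excludes subjects who have either at the pre-dose exam. Anything of that kind seen at one hour is therefore new, and a pre-dose to one-hour comparison would largely repeat the adverse event count. Dosing is also done by staff in confined subjects, with adverse events recorded throughout.

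A reader might also infer a known direction of bias. That is not supported either. Protocol 3.3 lists inadequate pain control, which might raise placebo withdrawals, alongside hypoxia, naloxone use, hypotension and persistent nausea, which might raise active-arm withdrawals.

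These arguments stand and limit the point. They leave the table itself as it is. Adverse event counts carry no denominator of subjects examined at a given time, the pooled row still mixes visits, and findings other than the excluded ones still lack a baseline.

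**Conclusion.** The dedicated table does not show on-treatment oral findings by arm, ignores the pre-dose exam, and pools visits at different distances from the last spray. The gap lies in the endpoint's own table and its denominators, because the adverse event tables remain a second route by arm. The size of any distortion cannot be stated from the documents beyond the bound of one expected subject per extra withdrawal, and its direction is unknown.

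Separately, irritation from repeated dosing that resolves before Follow-up may be missed by the scheduled exams in completers unless it is reported or noticed in passing. That is a limit to state when the results are read. The documents promise no end-of-dosing oral exam, so its absence is a design choice and not an inconsistency, and none is requested here.

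The timing range rests on twelve doses at 4-hour intervals and on the assumed clinic hours. Safety is descriptive (SAP 8.2.3) and the primary analysis is untouched. Severity: minor.

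**What to change.** In SAP 8.2.7, and in protocol 8.5.4.5 to match:
- Tabulate oral findings by arm in separate rows for pre-dose, one hour, Early Termination and Follow-up, each with the number examined.
- Report findings at the three post-dose exams as new or worsened against the pre-dose exam. If that exam is missing, the baseline rule in SAP 7.1 (last available value before treatment) already supplies the Screening exam.
- Carry the protocol's rule that new or worse oral findings are entered as adverse events into SAP 8.2.7, so that both documents describe the same two routes.

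The cost is a few lines of wording and revised table shells. All these exams are already scheduled and already due to be listed, so no new data or visit is needed. The SAP change is best made before database lock and unblinding.
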